# 2.2 Sample Size Determination

Up to 50 volunteers will be enrolled to allow targeted twenty-four (24) evaluable recovery endpoints.

In order to reach the total target number of evaluable subjects, additional subjects will be enrolled to replace subjects for whom the primary endpoints are not evaluable (i.e., those subjects who are lost-to-follow-up or withdrawn; those subjects whose health status has changed prior to their reinfusion, thereby potentially affecting their safety after receiving a reinfusion or potentially confounding study results; or those subjects for whom recovery calculations cannot be made due to missing value). All subjects, regardless of the availability of their endpoint data, will be included in evaluations of In vitro data (where samples are available) and in evaluations of AEs.

Estimates were prepared based on FDA criteria outlined in Section 1.4.1 with 24 subjects, examining the one-sided lower 95% confidence limit relative to the a priori value of 70%. Results are presented in the table presented below. If the observed proportion of treatment successes is 21/24 (87.50%) or higher, the one-sided lower 95% binomial confidence interval will exceed 70% (lower confidence limit = 70.77%).

Table 1: Statistical Scenarios 1-5 Estimation of LR-RBC Evaluation Sample Size

Scenario Number	1	2	3	4	5	6
Number of Treatment Successes	17/24	18/24	19/24	20/24	21/24	22/24
Percentage of Treatment Success	70.83	75.00	79.17	83.33	87.50	91.67
One-Sided Lower 95% Confidence Limit	52.13	56.53	61.09	65.82	70.77	76.02

Confidential Document

Doc No.: TMP-BS-01 Rev No.: 4.0

Statistical	Analysis	Plan	Template

Revision No. 1.0

Document Date: 28-Apr-2022

Page 10 of 17

Based on the binomial distribution, 24 evaluable LR-RBC products allow for 0, 1, 2 or 3 failures to establish 95% confidence that at least 70% of the products were successes.

If there are more than 24 evaluable recovery endpoints, then the allowable failure rate will be reevaluated to meet the FDA primary endpoint described in section 1.4.1. The following table shows the one-sided lower exact 95% confidence limits for the maximum allowable failure rate for different numbers of evaluable subjects.

Table 2: One-Sided Lower Exact 95% Confidence Limits for the Maximum Allowable Failure Rate

Number of Evaluable	Number of Treatment Successes	Number of Treatment Failures	Percentage of Success	Lower Confidence Limit
24	21	3	87.50	70.77
25	22	3	88.00	71.83
26	23	3	88.46	72.81
27	24	3	88.89	73.73
28	24	4	85.71	70.23
29	25	4	86.21	71.16
30	26	4	86.67	72.01

# 2.3 Study Populations

The Full Analysis Population will include all participants enrolled in the study and who met the eligibility criteria. Efforts will be made to obtain complete recovery data from all participants.

The Safety Analysis Population will include all participants enrolled in the study who met the eligibility criteria and were exposed to Reveos Blood Bag Set. The Safety Analysis Population will be utilized to assess safety of the device and procedure. It is possible for a volunteer to be included in the Safety Analysis Population more than once if they do not have an evaluable

Confidential Document

Doc No.: TMP-BS-01 Rev No.: 4.0

Revision No. 1.0

Document Date: 28-Apr-2022

Page 11 of 17

recovery endpoint. If this occurs, it will be noted in the relevant tables in the Clinical Investigation Report (CIR) though they will continue to be analyzed as separate participants.

The Evaluable Analysis Population will include participants who completed all study visits per protocol with a valid 24-hour recovery endpoint. The Evaluable Analysis Population will be used in the analysis of the primary endpoint. While the criteria allow for 20 or 24 participants, analysis will be based on all participants meeting the criteria of the Evaluable Analysis Population.

Data will be excluded from the Evaluable Analysis Population in the following situations:

- 1. Incomplete or incorrect procedure that affects the primary endpoint due to:
  - a. Equipment failure or malfunction (eg, filter plugs)
  - b. Unanticipated processing failure
  - c. Results of primary endpoint tests are not available
- 2. Protocol deviations that affect the primary endpoint due to:
  - a. Failure to follow collection procedures outlined in the device Operator's Manual, Instructions for Use (IFU) (Package Insert), Manual of Procedure(s), and site SOPs
- 3. Product non-reinfusable due to:
  - a. Product does not pass quality check for reinfusion (residual WBC, LR-RBC mass recovery, visual inspection, hemolysis, bacterial growth)
- 4. Participant issues
  - a. Participant lost to follow-up or withdrawn from study
  - b. Other participant issues (eg, inadequate access, reaction, needle abort)

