12.3 Participant Enrollment

A donor is considered an enrolled participant upon giving informed consent for study participation; this timepoint represents the beginning of a participant's involvement in the study. After informed consent has been obtained, participants will receive a unique subject identification number (USID) to de-identify participants. The USID number will use the following convention: XX-YYY, where XX is the pre-assigned site number and YYY will be a sequential number starting with 001. The USID number will be recorded on the Case Report Form (CRF). Participant identifiers such as initials or names will not be used, for example:

First participant enrolled at Site #01: John Doe = 01-001

First participant enrolled at Site #02: Jane Doe = 02-001

It is expected that some proportion of enrolled participants will not qualify for study inclusion per the screening and eligibility criteria, and some who are deemed eligible will not initiate the WB collection procedure. Participants will be considered study procedure discontinuations or study terminations if, following initiation of the WB collection, they do not complete the study procedures, as applicable and as described further in Section 13.

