19.1 Sample Size Rationale

The sample size in this study will be 24 evaluable subjects.⁷ In order to reach the total target number of evaluable subjects, additional subjects will be enrolled to replace subjects for whom the primary endpoints are not evaluable (i.e., those subjects who are lost-to-follow-up or withdrawn; those subjects whose health status has changed prior to their reinfusion, thereby potentially affecting their safety after receiving a reinfusion or potentially confounding study results; or those subjects for whom recovery calculations cannot be made due to missing value). It is anticipated that up to 50 donors may need to be enrolled to accrue 24 evaluable subjects to the primary endpoint analysis. All subjects, regardless of the availability of their endpoint data, will be included in evaluations of In vitro data (where samples are available) and in evaluations of AEs.

Sample Size Estimates for LR-RBC Evaluation

The 3 parts of FDA's RBC recovery criteria that must be met are presented below. The derivation of the sample size was based on the level of precision attained with 24 subjects relative to the 1st part of the criteria.

- 1. The one-sided 95% lower confidence limit for the population proportion of success is greater than 70% where success of a unit is defined as the RBC in vivo 24-hour percentage recovery $\geq 75\%^*$,
- 2. The sample mean of percent recovery \geq 75%, and
- 3. The sample standard deviation of in vivo 24-hour RBC recovery $\leq 9\%$.

*Allows for low recoveries (<75%) in 2/20 or 3/24 volunteers.

Estimates were prepared based on the 1st criterion (i) with 24 subjects, examining the one-sided lower 95% confidence limit relative to the a priori value of 70%. Results are presented in the table presented below. If the observed proportion of treatment successes is 21/24 (87.50%) or higher, the one-sided lower 95% binomial confidence interval will exceed 70% (lower confidence limit = 70.77%).

Scenario Number	1	2	3	4	5	6
Number of Treatment Successes	17/24	18/24	19/24	20/24	21/24	22/24
Percentage of Treatment Success	70.83	75.00	79.17	83.33	87.50	91.67
One-Sided Lower 95% Confidence Limit	52.13	56.53	61.09	65.82	70.77	76.02

Table 19-1	Statistical Scenarios	1-5 Estimation	of LR-RBC Evaluat	ion Sample Size.

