19.3.3 Evaluable Analysis Population

The analysis of the primary endpoint in the evaluable population will be based on all recorded data. Subjects are considered evaluable for the primary endpoints if they have:

- Met all of the inclusion and none of the exclusion criteria at enrollment,
- Were not found, after being enrolled in good faith, to be in fact, non-compliant with one or more of the inclusion/exclusion criteria,
- The subject has not had a change in health status which would cause them to fail the inclusion/exclusion criteria at the time of infusion of radiolabeled cells
- Have not met any other protocol exclusion criteria as defined in Section 19.4.

The Evaluable Analysis Population will be included in the analysis of the primary endpoint. Within the enrolled population, all attempts will be made to obtain complete recovery data from all subjects for the analysis of the primary endpoint.

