# 2.5.2 Safety Analyses

All adverse events collected will be provided for the Full Analysis Population by MedDRA system organ class and preferred term. Adverse event summaries for the purposes of device safety assessments will be limited to procedure-emergent adverse events (PEAEs), defined as any AE that occurs upon or after the exposure to the Reveos Blood Bag Set. PEAE summaries will be provided for the Safety Analysis Population.

Confidential Document

Doc No.: TMP-BS-01 Rev No.: 4.0

Revision No. 1.0

Document Date: 28-Apr-2022

Page 13 of 17

Tables will describe the frequency and percentage of all PEAEs, serious PEAEs, adverse device effects (ADEs), and unanticipated ADEs (UADEs). Additional presentations will summarize PEAEs by maximum reported severity; maximum relatedness to device, procedure, and medical history (related, not related); and those leading to discontinuation/termination. Concomitant medications used to treat PEAEs will also be summarized.

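### The SAP makes eligibility a condition of both adverse-event populations, so exposed participants later found ineligible may drop out of the safety tables, and screen failures cannot appear where the SAP says they will

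*SAP*

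**What the plan says.** SAP 2.3 defines the two populations that matter here.

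- Full: "The Full Analysis Population will include all participants enrolled in the study and who met the eligibility criteria".
- Safety: "all participants enrolled in the study who met the eligibility criteria and were exposed to Reveos Blood Bag Set".

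SAP 2.5.2 then assigns the adverse-event presentations. For the overall presentation it says "All adverse events collected will be provided for the Full Analysis Population". Summaries of procedure-emergent adverse events (PEAEs) go to the Safety population. A PEAE is "defined as any AE that occurs upon or after the exposure to the Reveos Blood Bag Set", with no mention of eligibility. No third population is named for adverse events.

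Protocol 12.3 fixes what enrolled means: "A donor is considered an enrolled participant upon giving informed consent for study participation". The same section expects some enrolled people not to qualify. Protocol 16.4.2 records adverse events from signature of the consent form.

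On who enters adverse-event evaluations, protocol 19.1 begins "All subjects, regardless of the availability of their endpoint data, will be included in evaluations of In vitro data". SAP 2.2 repeats that sentence, which closes "where samples are available) and in evaluations of AEs".

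Protocol 19.3.1 and 19.3.2 put no eligibility condition on either population. SAP section 4 sets the old and new definitions side by side and gives no specific reason for adding one.

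**The concern.** In the Full population the eligibility clause has an ordinary purpose: because enrolment happens at consent, it takes out screen failures. In the Safety population that purpose is already served, since someone who never reached collection was never exposed. Any further effect of the clause there can only be to remove people who were exposed to the bag set.

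A device safety table should count everyone exposed. If an exposed participant is left out, an event at collection in that person is missing from the PEAE, serious PEAE, adverse device effect and unanticipated adverse device effect tables, and the denominator shrinks by one. In a study aiming at 24 evaluable participants, a single event can be all there is to see.

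The clause also affects the Full population. A presentation described as covering every collected event, and a disposition summary that is to report screen failures, are both tied to a population that excludes screen failures by definition.

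**Working it through.** The plan states no figure on this point, so the check is one of set membership, followed by a small illustration.

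**Inputs.** Population definitions: SAP 2.3. Use of the populations: SAP 2.5.2 and 2.4.1. Meaning of enrolled: protocol 12.3. Order of Visit 2: protocol 13.2. Target of 24 evaluable and up to 50 enrolled: SAP 2.2.

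**Step 1: the sets.** Write E for enrolled, L for eligible, X for exposed.

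- Full = E and L.
- Safety = E and L and X, which is a subset of Full.
- A person in E and X but not L is in neither set, so no presentation in SAP 2.5.2 includes that person.
- A person in E but not L and not X (a screen failure before collection) is not in Full.

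**Step 2: when is L judged?** The SAP does not say.

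| Reading of the clause | Effect in Safety | Effect in Full |
|---|---|---|
| Passed the checks at Visits 1 and 2 | None: everyone properly exposed has passed | Removes screen failures |
| Judged on all information, including later findings | Removes exposed participants later found ineligible | Removes them and screen failures |

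On no reading does the clause add anything useful to the Safety definition.

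**Step 3: can the second case arise?** Protocol 19.3.3 provides for it when it limits the Evaluable population to people who "Were not found, after being enrolled in good faith, to be in fact, non-compliant with one or more of the inclusion/exclusion criteria". Protocol 11.1 says that medical history is self-reported and that no medical records are accessed, so a late discovery is plausible. Protocol 13.2 also allows the viral screen at Visit 2, where it is listed (step 5) after collection into the bag set (step 4). That route is weaker, because protocol 13.2 and 13.6 label a positive screen a withdrawal.

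**Step 4: illustration.** The documents give no count of exposed participants later found ineligible. Assume one, with one event, and no such event in anyone else.

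- 24 evaluable + 1 = 25 exposed. All exposed: 1/25 = 4.0%. Under the second reading: 0/24 = 0%.
- Upper end: if at least one of 50 enrolled does not reach collection, at most 49 are exposed. All exposed: 1/49 = 2.0%. Under the second reading: 0/48 = 0%.

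The first case also assumes no other exposed but non-evaluable participant.

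**Step 5: the Full population.** This step does not depend on Step 2. Adverse events are recorded from consent, so some may belong to screen failures, and those cannot be shown in Full. SAP 2.4.1 summarises enrolment using Full and promises a number and percentage of screen failures. Full contains none, and no other denominator is given.

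**The case against.** The best defence is that the clause means judged eligible at the time. Eligibility is confirmed at Visit 1 and again as step 1 of Visit 2, before collection. Protocol 19.3.3 lists meeting the criteria at enrolment and not being found non-compliant later as separate conditions, which suggests that meeting the criteria need not include late discovery. This reading is reasonable and keeps the person in. However, SAP 2.3 does not carry over the words that tie the condition to enrolment, and two programmers could build different safety sets from it.

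Next, protocol 12.3 classes people who stop after collection has begun as discontinuations or terminations, not screen failures, and SAP 2.5.2 plans a summary of PEAEs leading to discontinuation or termination. This shows an expectation that such people are in the safety tables. It does not settle the matter, because the label does not make anyone eligible under SAP 2.3.

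The sentence in SAP 2.2 and protocol 19.1 that brings all subjects into adverse-event evaluations also points towards inclusion. It concerns the availability of endpoint data rather than eligibility, so it is in tension with SAP 2.3 and does not override it.

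Finally, screen failures before collection were never exposed, and protocol 16.4.2 limits the safety analysis to PEAEs. Leaving out their events therefore costs no device-safety information. That is correct. What remains is that the SAP promises a presentation and a percentage that its own population cannot supply.

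**Conclusion.** The point holds as a defect of definition. In the Safety population the eligibility clause is either redundant or removes exposed participants, and the SAP does not say which. In the Full population it contradicts the all-events presentation and the screen-failure disposition whichever reading is taken.

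The effect is probably small. The illustration of 1/25 against 0/24 (or 1/49 against 0/48) rests on the assumption of one late-found ineligible participant with one event, and nothing in the documents says that this will happen.

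A reader might infer more than the text supports:

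- That the SAP definitely excludes exposed participants. It does so only if eligibility is judged with hindsight.
- That a participant whose health changes after entry is removed. Read as entry eligibility, the clause does not do this; SAP 1.2 and protocol 19.3.3 treat a change in health status as a separate matter of evaluability.
- That a positive viral screen after collection certainly removes someone. The protocol calls it a withdrawal, so this depends on how the clause is applied.
- That the difference between up to 50 enrolled and 24 evaluable measures the loss. That difference mixes screen failures with withdrawals, failed units and loss to follow-up.
- That safety data are lost. Events remain on the case report form (protocol 16.5), serious events and unanticipated device effects still reach the sponsor within 24 hours (protocol 16.8), and the disposition listing shows who was left out of which population (SAP 2.4.1), though not their events.

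The primary analysis is untouched.

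**What to change.** - SAP 2.3: define the Safety Analysis Population as every enrolled participant exposed to the Reveos Blood Bag Set, regardless of eligibility.
- SAP 2.5.2 and 2.4.1: present all collected adverse events, and disposition, for all enrolled (consented) participants, which is the group in protocol 19.3.1. Use that group as the denominator for screen failures.
- Do not go back to the Safety definition in protocol 19.3.2. It admits only participants with a related adverse event and so cannot serve as a denominator.
- As an editorial follow-on, SAP 2.1 should describe the size shown in each table as that of the population used, since it currently explains it as the number enrolled.

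The cost is wording in four SAP sections and the matching table shells. Study conduct, sample size and the primary analysis do not change.

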# 2.4 Participant Accounting and Baseline Characteristics

# 2.4.1 Participant Disposition

Enrollment and level of participation in the study will be summarized using the Full Analysis Population. The number and percent of participants per population will be summarized for each analysis population. The number and percentage of participants will also be presented for those participants who were screen failures or otherwise discontinued the study early and the reason for discontinuation will be noted.

Participant disposition data will be provided in a listing, which will cover each participant's eligibility for study participation as well as inclusion in or exclusion from each of the analysis populations (including enrollment and completion of study procedures, and/or evaluability).

Confidential Document

Doc No.: TMP-BS-01 Rev No.: 4.0

Revision No. 1.0

Document Date: 28-Apr-2022

Page 12 of 17

# 2.4.2 Participant Characteristics

Demographic and baseline characteristics will be provided in the listings for the Full Analysis Population and will be summarized for the Full Analysis Population, Safety Analysis Population, and Evaluable Analysis Population. Vital signs will be summarized for the Safety Analysis Population and laboratory results will be summarized for the Evaluable Analysis Population.

### 2.4.3 Clinical Investigation Plan Deviations

A listing of CIP deviations will be provided by the Sponsor.

#### 2.4.4 Device Deficiencies

A listing of Device Deficiencies will be provided by the Sponsor.

#### 2.5 Analyses

### 2.5.1 Primary Endpoint Analysis

The analysis of the primary endpoint will be conducted using the Evaluable Analysis Population.

The primary endpoint of RBC recovery at 24 hours post-infusion will be used to assess each of the three criteria specified by FDA. To assess the criteria associated with the percent of samples with at least a 75% recovery, a success or failure for each observed value will be determined. RBC recovery of at least 75% will be deemed a success, and failure otherwise. A one-sided confidence interval for the proportion of successes will be determined using the Clopper-Pearson exact method for a 95% confidence interval. If the one-sided 95% lower confidence limit is greater than 70% the study will have met its primary endpoint. Summary statistics will be presented to assess the actual RBC recovery values to evaluate the remaining criteria specified by FDA.

Primary endpoint will be reported with single label 24-hour endpoint recovery method. Dual label 24-hour recovery endpoint will also be reported as an exploratory method.

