6 CLINICAL TRIAL EXPERIENCE

The investigational Reveos System intended for US market does not have clinical trial experience.

7 **RATIONALE FOR THE CURRENT STUDY**

Terumo Blood and Cell Technologies is seeking 510(k) clearance from FDA/CBER for the Reveos® Automated Blood Processing System (Reveos System).

The proposed study will provide validation on the in vivo performance of LR-RBC units derived from WB processed with the Reveos System. The results will provide data as to whether the Reveos System produced LR-RBC can maintain required levels of 24-hour in vivo recovery that meet FDA criteria for RBC.⁷

8 **OBJECTIVES**

8.1 **Primary Objective**

The primary objective of this study is to evaluate whether the LR-RBC derived from WB processed with the Reveos System meet FDA criteria for in vivo 24-hour recovery.

Based on FDA criteria for in vivo RBC quality, the following criteria will be assessed:

LR-RBC mean 24-hour recovery $\ge 75\%$ with SD $\le 9\%$ and one-sided lower confidence limit for population proportion of RBC in vivo recovery 70%[†]. Success is >75%.

†Allows for low recoveries (<75%) in 2/20 or 3/24 volunteers.

If all three criteria are met, the Reveos System will be deemed to have met the FDA criteria for 24-hour in vivo RBC recovery.

Performance criteria will be evaluated in healthy adult participants, who receive radiolabeled, autologous infusions of LR-RBC components after being stored for 42 days at 1-6°C.

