9 ENDPOINTS

9.1 **Primary Endpoint**

The primary endpoint is the 24-hour in vivo RBC recovery.

LR-RBC mean 24-hour recovery \geq 75% with SD \leq 9% and one-sided lower confidence limit for population proportion of RBC in vivo recovery 70%[†]. Success is >75%.

†Allows for low recoveries (<75%) in 2/20 or 3/24 volunteers.

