The primary endpoint of RBC recovery at 24 hours post-infusion will be used to assess each of the three criteria specified by FDA. The % recovery for analysis will be provided by the site(s), and not derived during analysis. To assess the criteria associated with the percent of samples with at least a 75% recovery, a success or failure for each observed value will be determined. RBC recovery of at least 75% will be deemed a success, and failure otherwise. A one-sided confidence interval for the proportion of successes will be determined using an exact 95% confidence interval. If the one-sided 95% lower confidence limit is greater than 70% the study will have met its primary endpoint, which will be met if no more than 3/24 data points have less than 75% recovery.

Summary statistics and 2-sided confidence intervals will be presented to assess the actual RBC recovery values and to evaluate the remaining criteria specified by FDA.

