#### 1.4 Outcome Measures

### 1.4.1 Primary Endpoint

The primary endpoint is the 24-hour in vivo RBC recovery. The FDA criteria requires LR-RBC mean 24-hour recovery  $\geq$ 75% with standard deviation (SD)  $\leq$  9% and a one-sided lower confidence limit for the population proportion of RBCs in vivo recovery of 70% with a "success" being LR-RBC recovery >75%. This allows for low recoveries (<75%) in 2/20 or 3/24 volunteers.

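### The primary endpoint is declared met on the success proportion alone, although the primary objective also requires the mean and SD criteria

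*SAP*

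**What the plan says.** SAP 2.5.1 and protocol 19.2.1 both begin by saying that 24-hour recovery will be used to assess each of the three FDA criteria. Both then give a decision rule on one of them. The SAP says: "If the one-sided 95% lower confidence limit is greater than 70% the study will have met its primary endpoint". The protocol uses the same limit and adds the matching failure count: "the study will have met its primary endpoint, which will be met if no more than 3/24 data points have less than 75% recovery". The mean and SD come in the following sentence, which in the SAP reads: "Summary statistics will be presented to assess the actual RBC recovery values to evaluate the remaining criteria specified by FDA". The protocol's version adds two-sided confidence intervals. Neither states a consequence if the mean or SD criterion fails.

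Other sections treat the three criteria as a set:

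- Protocol 8.1: "If all three criteria are met, the Reveos System will be deemed to have met the FDA criteria for 24-hour in vivo RBC recovery".
- Protocol 19.1: "The 3 parts of FDA's RBC recovery criteria that must be met are presented below".
- The protocol synopsis, protocol 9.1 and SAP 1.4.1 state the mean, SD and proportion criteria together, the last two under the heading of the primary endpoint.

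SAP 2.2 adds that with more than 24 evaluable results, "then the allowable failure rate will be reevaluated to meet the FDA primary endpoint described in section 1.4.1". SAP section 4, which lists changes from the protocol, records no intention to drop the three-part rule.

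**The concern.** This is the study's only confirmatory conclusion, and the documents contain two rules for it. Protocol 8.1 governs when the system is deemed to meet the FDA criteria. SAP 2.5.1 and protocol 19.2.1 govern when the study is said to have met its primary endpoint. The SAP never says in its own text that all three criteria must hold.

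The rules can disagree because a count of recoveries below 75% ignores how far below they fall, while the mean and SD do not. If the SD came out above 9% with no more than three failures, the sponsor would hold data with two written and opposite conclusions and would have to choose between them after seeing the result. Protocol 8.1 would still deny that the FDA criteria were met, so the outcome is a contradiction and not an unqualified claim of success.

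**Working it through.** **Inputs.** N = 24 evaluable (protocol 19.1). Individual success is recovery of at least 75%, and the limit is Clopper-Pearson, one-sided 95% (SAP 2.5.1). The thresholds are mean at least 75% and sample SD at most 9% (protocol 19.1). The sample size rests on the proportion criterion only, and no expected mean or SD of recovery is given.

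**1. The plan's own figure.** The lower limit for x successes in n is the 5th percentile of a Beta(x, n − x + 1) distribution.

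- 21/24: Beta(21, 4) gives 70.77%.
- 20/24: Beta(20, 5) gives 65.82%.

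Both agree with protocol Table 19-1 and SAP Table 1. The proportion rule at N = 24 is therefore at most three failures.

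**2. Does passing the proportion rule secure the other two criteria?** Take 21 recoveries equal to a and three equal to y. Then

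- mean = (21a + 3y)/24
- SD (n − 1 divisor) = (a − y) × √(21 × 3/(24 × 23)) = 0.3378 × (a − y)

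The SD exceeds 9% once a − y exceeds 9/0.3378 = 26.64 points.

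| Data (24 values) | Lower limit | Mean | SD | Proportion rule | All three |
|---|---|---|---|---|---|
| 21 at 84%, 3 at 50% | 70.77% | 79.75% | 11.49% | met | SD fails |
| 21 at 76%, 3 at 60% | 70.77% | 74.00% | 5.41% | met | mean fails |

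With the successes at 84%, the SD criterion fails once the three low values lie below 84 − 26.64 = 57.4%. With the successes at 76%, the mean fails once they lie below (24 × 75 − 21 × 76)/3 = 68%. So the proportion rule implies neither of the other criteria.

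**3. How often might the rules disagree?** I simulated 400,000 trials of 24 for each assumed distribution.

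| Assumed recovery distribution | P(proportion rule met) | P(all three met) | Gap (points) |
|---|---|---|---|
| Normal, mean 82, SD 6 | 0.67 | 0.67 | 0 |
| Normal, 84, 7 | 0.79 | 0.78 | 1 |
| Normal, 84, 8 | 0.62 | 0.56 | 6 |
| Normal, 84, 8, truncated at 100% | 0.60 | 0.59 | 1 |
| Normal, 86, 9 | 0.73 | 0.46 | 26 |
| Normal, 86, 9, truncated at 100% (SD becomes 8.0) | 0.69 | 0.64 | 4 |
| Normal, 88, 10 | 0.80 | 0.26 | 54 |
| Normal, 88, 10, truncated at 100% (SD becomes 8.3) | 0.74 | 0.64 | 9 |
| Mixture: 92% normal (84, 5), 8% normal (58, 8); overall SD 8.8 | 0.72 | 0.52 | 20 |

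The untruncated rows for (86, 9) and (88, 10) put about 6% and 11–12% of draws above 100% recovery, so their gaps of 26 and 54 points should carry no weight. In every row the whole gap comes from the SD criterion. No simulated trial passed the proportion rule and failed the mean.

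**4. SAP 2.2.** Its Table 2 lists the failure count allowed at each N from 24 to 30. That count answers the proportion criterion. The endpoint to which the sentence refers, in SAP 1.4.1, also includes the mean and SD, which a failure count cannot establish.

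**The case against.** The strongest reply is that the documents, read as a whole, do require all three. Protocol 8.1 says so, protocol 19.1 says the parts must be met, and SAP 1.4.1 lists them under the primary endpoint. SAP 2.5.1 opens with the three criteria and closes with the remaining ones, so its decision sentence may only be loose drafting that wrote primary endpoint where this criterion was meant. All three quantities will be computed and reported, so a failed SD would be visible.

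That is probably how the sentence arose, and it is right that no analysis is missing. It does not remove the conflict. Evaluating the remaining criteria is not the same as making the conclusion depend on them, and by then the preceding sentence has already declared the endpoint met.

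Three further points stand in part:

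- The probabilities rest on assumed distributions, and the low-recovery component of the mixture has no basis in the documents.
- The mean criterion adds little in practice. Failing it after passing the proportion rule needs the successes bunched just above 75%.
- The SAP 2.2 sentence can fairly be read as concerning the failure count only. It needs clarifying and is a minor part of the point.

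**Conclusion.** The concern holds. The decision rule in SAP 2.5.1 and protocol 19.2.1 contradicts the three-part primary objective in protocol 8.1, and it should be corrected before the data are analysed. That follows from the text and from the constructed data sets, and needs no distributional assumption.

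The chance of a discordant result is unknown, because the documents give no expected mean or SD. On the assumed distributions that keep recovery at or below 100%, or nearly so, it is negligible when the true SD is about 6%, between 1 and 9 points for truncated normal distributions with SD of about 7.5% to 8.3%, and about 20 points if occasional very low recoveries bring the overall SD to 8.8%. These are illustrations and not bounds. The practical exposure is the SD criterion.

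**What to change.** In SAP 2.5.1 and protocol 19.2.1, replace the decision sentence with one to this effect: the primary endpoint is met only if, in the Evaluable Analysis Population, the one-sided exact 95% lower limit for the proportion of successes is above 70%, the sample mean recovery is at least 75% and the sample SD is at most 9%; if any one fails, the endpoint is not met. In protocol 19.2.1, the 3/24 remark should be tied to the proportion criterion only.

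In SAP 2.2, add a clause that the 21/24 calculation and Table 2 concern the proportion criterion alone. Protocol 19.1 already says this of its own calculation and can stay as it is.

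The cost is one sentence in each document and one clause in the SAP. N = 24, the 3/24 allowance, the interval method and study conduct do not change. The chance of declaring the endpoint met falls if the true SD is near or above 9%, and is essentially unchanged if it is about 6% or less. Neither document states a chance of success, so no stated figure has to be revised.
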